5.7. Safety

Safety assessment criteria will be used to:

- Treatment discontinuations and reasons for this,
- Adverse events and any complications recorded prospectively (graded according to the 'Common Terminology Criteria for Adverse Events' (CTCAE) version 4.0, dated May 2009).

These criteria will be shown descriptively in the safety analysis set.

The analyses of adverse events will be performed twice on the safety analysis set:

- by treatment group at inclusion;
- by group in which treatment was received at least once during the study. In this analysis, the AE will be attributed to ongoing treatment at the start of the AE. An AE beginning after a treatment was discontinued could be attributed to the treatment depending on the rules shown in the table below.

Prior to the safety analysis, the number of patients who received the treatment at least once in the group (targeted therapy/other treatments) and in the treatment subgroups will also be presented. Exposure for each treatment group and subgroup will be calculated.

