The adverse events will also be described by treatment group, in patients who received treatment at least once during the study (targeted therapies/other treatments; the other treatments will also be described depending on whether these involved chemotherapy/somatostatin analogs/others) by System Organ Class (SOC) and Preferred Term (PT). The same analysis will be presented for adverse events with a suspected relationship with the study treatment, grade 3 adverse events with a suspected relationship with the study treatment, serious grade 3 adverse events with a suspected relationship with the study treatment, adverse events grade =3, adverse events ≥4, for serious adverse events, non-serious adverse events, serious grade =3 adverse events, adverse events which resulted in temporary discontinuation of treatment, adverse events which resulted in permanent discontinuation of treatment and adverse events which resulted in the death of patient.

In terms of the analysis by treatment received during the study, several rules have been defined:

The denominator will be the number of patients who received the ongoing treatment during the prospective period at least once. In the case of combination treatments, the treatments will be separated and the patient will be counted several times.

The AE will be deemed to be on treatment until 28 days after the treatment is stopped. Similarly, if the investigator links an AE to a treatment, this will also be counted on this related treatment (regardless of the dates the treatment is taken).

If the treatment is still ongoing at the time of last news, the AE will be deemed to be on treatment for up to 28 days after the date of last news.

Amongst the "other" treatments, Lutathera treatment will be deemed to be metabolic radiotherapy.

If the date of onset of the adverse event is missing:

- If the day of the event is missing, the event will be attributed to all treatments received during the month when the AE was declared.
- if the day and month of the event are missing, the event will be attributed to all treatments during the year in which the AE is declared unless the treatment was received after the end of the AE.

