For combination treatments, the start and end date of the combination were not recorded in the CRF. The visit immediately before the report of the additional combination will therefore be deemed to be the start date and the visit corresponding to discontinuation of the combination will be deemed to be the end date of the combination, unless the combination began or finished during a treatment line (where start and end dates are reported). The 28-day rule also applies to combination treatments.

The AEs will be analysed as follows:

	Actual exposure	Actual exposure +28 days	Treatment reported in the "Causality with the study treatment" column
At least one adverse event		X	
At least one serious adverse event		X	
At least one adverse event with a suspected relationship with the study treatment			X
At least one adverse event resulting in death		X	
At least one adverse event leading to permanent discontinuation of treatment	X		
At least one adverse event leading to change in dosage/temporary discontinuation of treatment	X		
At least one adverse event with a suspected relationship with the study treatment leading to permanent discontinuation of treatment	X		X
At least one adverse event with a suspected relationship with the study treatment leading to adjustment of dosage/temporary discontinuation of treatment	X		X
At least one adverse event with a suspected relationship with the study treatment leading to temporary discontinuation of treatment	X		X
At least one serious adverse event with a suspected relationship with the study treatment leading to permanent discontinuation of treatment	X		X
At least one serious adverse event grave with a suspected relationship with the study treatment leading to adjustment of dosage/temporary discontinuation of treatment	X		X
At least one serious adverse event with a suspected relationship with the study treatment leading to temporary discontinuation of treatment	X		X

^{*} AEs on treatment analysed as reported in the actual exposure and in the "causality with the study treatment" column.

Adverse events will be listed overall, together with the grade ≥ 3 adverse events, serious adverse events, adverse events with a suspected relationship to the study treatment leading to permanent discontinuation of the treatment and adverse events with a suspected relationship to the study treatment leading to temporary discontinuation of the treatment.

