NB: the listings will show the retrospective adverse events and the prospective adverse events, whereas the summary tables will only include the prospective adverse events.

The listing of adverse events reported in patients excluded from the safety analysis set will be provided where applicable.

Handling of missing data:

If the seriousness (serious/non-serious) and/or causality with the treatment are missing, the most adverse situation for treatment is assumed in the summary tables, i.e. a serious case and/or one related to the study treatment.

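### In the by-treatment-received AE tables, the related-AE percentages can count patients who are not in that drug's denominator

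*SAP*

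**What the plan says.** SAP 5.7 plans the AE analyses twice on the safety analysis set: once by treatment at inclusion, and once "by group in which treatment was received at least once during the study". Only the second is at issue. SAP 5.7.2 gives its rules:

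- Denominator: "The denominator will be the number of patients who received the ongoing treatment during the prospective period at least once". Combinations are split into their components, so one patient may appear in several columns.
- Time window: "The AE will be deemed to be on treatment until 28 days after the treatment is stopped".
- Causality: where the investigator attributes an event to a drug, the rule is that "this will also be counted on this related treatment (regardless of the dates the treatment is taken").

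The table after these rules shows which criterion each output row uses. The row "At least one adverse event with a suspected relationship with the study treatment" is ticked under the causality column only. The all-AE, serious and fatal rows are ticked under exposure plus 28 days. The related-AE rows that lead to stopping or adjusting treatment are ticked under both actual exposure and causality.

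The section also says that "the summary tables will only include the prospective adverse events", with retrospective events shown in the listings.

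**The concern.** A percentage of patients needs every numerator patient to be in the denominator. Here the denominator carries an exposure condition (drug taken in the prospective period), and the causality-only numerator has none. If the two diverge, the printed figure is not a proportion of the N at the head of its column. The error has one direction: it can only raise the drug's related-AE percentage.

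Safety is part of the primary objective (SAP 5.5). The AE overview templates print patient percentages under a column N, with everolimus and sunitinib in separate columns, so a reader would take these figures as drug-specific related-AE rates.

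**Working it through.** The plan gives no figure to reproduce. The check is mainly one of logic, followed by a short illustration.

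**1. The two conditions side by side, for the causality-only row**

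| | Condition on the AE | Condition on the drug |
|---|---|---|
| Numerator | Prospective; linked to the drug | None on dates |
| Denominator | None | Taken at least once in the prospective period |

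No sentence in SAP 5.7 or 5.7.2 requires the numerator patient to meet the denominator's condition.

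**2. Can a patient meet the first condition and not the second?** Yes. Patients may be included on lines one to four, so they may have up to three earlier lines. The exclusion in SAP 3.3 and Protocol 5.1.2 covers only a targeted drug that the patient has already received and is now taking again. A patient included on everolimus may have had sunitinib earlier, and the reverse. The SAP expects such patients: 5.9.1 splits the population by targeted therapy before inclusion, and 5.9.7 compares two or more with one before inclusion. Earlier chemotherapy or somatostatin analogues give the same route.

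**3. Does the prospective-AE restriction close the route?** No. It dates the event, not the drug. It does narrow the route to one pattern: a drug stopped before inclusion and not taken again, followed by a post-inclusion AE linked to it. Prevalent patients on their current line are not affected, because that treatment is ongoing at inclusion and they are in its denominator.

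**4. Which outputs are exposed?** The causality-only row and, by extension, its grade-specific versions (Table 14.3.2.2) and the related-AE tables by SOC and PT (Tables 14.3.2.4 and 14.3.2.8 to 14.3.2.10), in the by-treatment-received versions. In the two-group columns, a patient who switched from sunitinib to everolimus is already in the targeted-therapy denominator. That switch therefore matters only in the columns by individual drug.

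**5. Size.** Let N be the column denominator, x the related-AE patients inside it, and k the related-AE patients outside it.

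- As written: (x + k)/N, so each outside patient adds 1/N.
- Numerator restricted to the column: x/N.
- Outside patients also added to the denominator: (x + k)/(N + k).

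Take N = 35, the planned minimum per targeted drug (SAP 3.3), and assume x = 21:

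| k (assumed) | As written | Restricted | Added to both |
|---|---|---|---|
| 0 | 21/35 = 60.0% | 60.0% | 60.0% |
| 1 | 22/35 = 62.9% | 60.0% | 22/36 = 61.1% |
| 2 | 23/35 = 65.7% | 60.0% | 23/37 = 62.2% |

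The increment per patient is 1/35 = 2.9 points. At an assumed N of 10 it is 1/10 = 10 points. In the extreme case x = 35, k = 1, the rule gives 36/35 = 102.9%, which shows that the quantity is not a proportion.

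**The case against.** The best defence is that the column population is already fixed. SAP 5.7 defines this analysis by treatment received during the study, and 5.7.2 describes the SOC/PT tables as "in patients who received treatment at least once during the study". The denominator and causality rules sit under one introduction about treatment received during the study. On that reading the causality rule only waives the 28-day limit for late events in patients already in the column. It follows the 28-day rule directly, and SAP 5.7 says that events starting after discontinuation may be attributed to a treatment.

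A second argument is that the causality field refers to the study treatment, while Protocol Table 3 places earlier treatments under history. An investigator might then have no way to link a prospective AE to a drug stopped before inclusion. The option list in the CRF's AE table is incomplete in the text available, so this cannot be settled.

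The first argument shows that a sensible reading exists. It does not make that reading a rule: the scope wording never restricts the numerator, and it stands against an explicit instruction to ignore the dates. Two competent programmers could print different figures. The second argument bears on how often the problem arises, not on whether the rules agree.

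The objection is right about scope and size. Most rows are protected by their exposure conditions. The figure of 35 is a recruitment minimum by drug at inclusion, not this denominator, which also counts patients who receive the drug in later lines or combinations.

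**Conclusion.** The gap is real and minor. Followed literally, the causality-only related-AE row and its grade and SOC/PT counterparts, in the by-treatment-received tables, can include patients outside the denominator.

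The number of such patients is unknown and probably small. Each adds at most 2.9 points if the drug's denominator is at least 35. That holds if the recruitment minimum was met, which is not assured because Protocol 5.1 closes recruitment on a fixed date regardless of numbers. Smaller columns move more.

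Three stronger readings are not supported:

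- **That AE percentages by drug are inflated in general.** The row table ties the all-AE, serious and fatal rows to exposure plus 28 days, and the related-AE rows on stopping or adjusting treatment to actual exposure as well. Tables by treatment at inclusion are untouched. This takes the row table as governing; the prose causality rule, read alone, is broader.
- **That the bias is some 3 to 6 points.** This needs one or two such patients in a column of 35 (1/35 = 2.9, 2/35 = 5.7), and the documents give no count.
- **That events before inclusion enter the percentages.** Retrospective AEs are kept out of the summary tables.

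**What to change.** Add one sentence to SAP 5.7.2: in the analysis by treatment received, each column's numerator is restricted to patients in that column's denominator. Keep the causality rule without a date limit for those patients, so that late related events more than 28 days after stopping still count.

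Report prospective AEs linked to a drug received only before inclusion in Listing 16.2.6, which already shows causality and the treatments received at onset, and give their number in a footnote to the affected tables. In the same edit, state that the row table governs where the prose causality rule is broader, notably for the all-AE row.

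Adding the outside patients to the denominator is a weaker remedy. Only earlier users who had a linked event would be added, so the denominator would depend on the outcome.

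The cost is one sentence, one programming filter and a footnote. There is a small downside: a few investigator-attributed events leave the drug's summary percentage, though they remain listed and counted.

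### When an AE's onset day is missing, the SAP's month rule does not carry over the 28-day post-stop window that its any-AE, SAE and fatal-AE rows use

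*SAP*

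**What the plan says.** SAP 5.7 runs the AE analysis twice, by treatment group at inclusion and by treatment received at least once during the study. Only the second uses the attribution rules discussed here. For AEs that start after a drug was stopped, it points to the table in 5.7.2: "An AE beginning after a treatment was discontinued could be attributed to the treatment depending on the rules shown in the table below".

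SAP 5.7.2 then gives these rules.

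- Full onset date: "The AE will be deemed to be on treatment until 28 days after the treatment is stopped". For add-on drugs, "The 28-day rule also applies to combination treatments".
- Table of rows: any AE, any SAE and AE resulting in death fall under "Actual exposure +28 days". Two rows (AEs leading to permanent discontinuation, and to dose change or temporary discontinuation) use actual exposure alone. One uses reported causality alone, and six use actual exposure together with causality.
- Causality: for an AE that the investigator links to a treatment, "this will also be counted on this related treatment (regardless of the dates the treatment is taken". If causality is missing, "the most adverse situation for treatment is assumed in the summary tables".
- Onset day unknown: "If the day of the event is missing, the event will be attributed to all treatments received during the month when the AE was declared".
- Onset day and month missing: all treatments of the year of declaration, "unless the treatment was received after the end of the AE". The missing-day rule carries no such exception.

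The SAP does not say how the partial-date rules interact with the 28-day rule. It also does not say whether *declared* means the month the AE began or the month it was reported.

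**The concern.** The 28-day test needs an onset date. When the day is missing, the month rule is the only date rule left to apply, and it refers to drugs *received* in the month. Two other places in the SAP favour reading *received* without the 28-day tail. Listing 16.2.6 has one entry for treatments received at onset and a separate one for treatments deemed to be received under the 28-day limit. The day-15 substitution in SAP 4.5 could have turned a month into a date, but its heading confines it to calculating time periods. A programmer who follows the text could therefore drop a drug stopped at the end of the previous month.

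At stake are the any-AE, SAE and fatal-AE counts by treatment received. Their grade ≥3 and SOC/PT versions follow, because SAP 5.7.2 asks for the same information for those events. These rows are meant to count events whatever their cause, and safety is part of the primary objective (Protocol 3.1, SAP 5.5). SAP 5.5.1 notes that treatment is usually changed after progression, so stops followed by a new drug will be common. Protocol section 7 also runs AE notification to at least 28 days after the last administration, so events in this window are collected on purpose.

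**Working it through.** The documents give no figure for this rule, so there is none to reproduce. The check asks how often a true onset within 28 days of stop falls in a later calendar month than the stop.

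**Inputs.** Window of 28 days (SAP 5.7.2). Assumptions: stop dates uniform over 2016–2019 (1,461 days, 48 months, mean month 1,461/48 = 30.4375 days); true onset uniform on days 1 to W after stop; day missing, month known.

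**Formula.** At lag k ≤ 28 days, onset is in the next month exactly when the stop is in the last k days of its month. That has probability k/30.4375. Averaging over k = 1…W gives

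share in next month = ((W + 1)/2) / 30.4375.

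| True onset within W days of stop | Calculation | Share in next month |
|---|---|---|
| 7 | 4.0/30.4375 | 13.1% |
| 14 | 7.5/30.4375 | 24.6% |
| 21 | 11.0/30.4375 | 36.1% |
| 28 | 14.5/30.4375 | 47.6% |

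Enumerating all 1,461 × 28 = 40,908 pairs of stop and onset dates gives the same values: 47.6% in the next month and 52.4% in the stop month.

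**Examples.**

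- Stop 31 March, onset 5 April, 5 days later. With the full date the AE is on treatment. With only April known, the literal rule omits the stopped drug.
- Stop 30 May. The window runs to 27 June, so 27 of June's 30 days are inside it, yet an AE dated only to June is not counted on the drug.
- Stop 5 March, onset 20 March, day missing. The stopped drug keeps the AE, which is also counted on any other drug received in March.

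**Effect of an overlap rule.** Suppose a drug counts when any day of the onset month lies between its start and stop + 28 days. No AE truly within 28 days is then lost. The cost is over-attribution. At lag 28 + j, the stopped drug is also counted when the onset's day of the month is at least j + 1, which has probability about 1 − j/30.4375. Over j = 1…32 (days 29 to 60) this averages (30 − 465/30.4375)/32 = 14.72/32 = 46%, because the terms beyond j = 30 are zero. Enumeration also gives 46%.

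**Effect of using day 15 instead.** Per month, the lost pairs number 1 + 2 + … + 28 = 406. Imputing the 15th puts onset inside the window when the stop is in the last 14 days of its month. That covers (1 + … + 14) + 14 × 14 = 105 + 196 = 301 pairs. So 301/406 = 74% of the lost cases are recovered and 26% are not.

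**The case against.** A reader might infer that the SAP overrides its own 28-day rule for partial dates and moves toxicity from the stopped drug to its successor. The documents do not support that.

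- The missing-day sentence does not say *only* and sets no precedence. The 28-day rule and the table of rows stand beside it without an exception for partial dates, so the rules can be read together. Listing 16.2.6 makes the narrow reading likely but does not settle it.
- AEs that the investigator links to the stopped drug stay on it whatever the dates, and missing causality counts as related. What can be lost are AEs not linked to that drug. This safeguard is partial: the three rows at issue are not meant to depend on causality, and SAP 6.2 admits that for combinations the doctor can enter only one treatment.
- Nothing is moved to the next drug. A successor received in the onset month is counted under the literal rule and under the fix alike. At most the stopped drug loses a count. If no drug was received that month, the AE is counted on none.
- Only three of the twelve table rows use the 28-day tail.

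A reader might also extend the point to the year-only rule. That does not hold. A drug stopped on 31 December has a window to 28 January, at most 28/365 = 7.7% of the next year, so leaving it out is usually right. An overlap rule there would do harm: a drug stopped on 4 December has a window ending on 1 January and would take every AE dated only to the following year.

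On *declared*, the sentence sits under a heading about missing onset dates, so onset month is a natural reading. But Protocol section 7 uses the word for reporting to pharmacovigilance, and the CRF asks about AEs since the last visit, with visits about every 2–3 months. The two months can differ, so the word should be settled.

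**Conclusion.** The point holds in a limited form. Applied as written, the missing-day rule can leave out a stopped drug that the SAP's own 28-day rows would include. It affects AEs not linked to that drug, with true onset within 28 days of stop but in the next calendar month, in the any-AE, SAE and fatal-AE counts by treatment received and their grade ≥3 and SOC/PT versions.

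Among unlinked post-stop AEs with a missing day, the share affected is about 48% if onset is uniform over the 28 days and 13–36% if onset is within 7–21 days. These shares assume stop dates spread evenly over the calendar. They are not shares of all AEs. The number of AEs with a missing onset day is not given, so no effect on any table can be stated, and it may be small. The rule also runs against the SAP's principle for missing seriousness and causality, which is to assume the worst case for the treatment.

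**What to change.** Replace the missing-day sentence in SAP 5.7.2 with a rule to this effect: if the onset day is missing, attribute the AE, row by row, to every treatment whose analysis window for that row overlaps at least one day of the onset month, except treatments started after the AE ended. The window is exposure plus 28 days for the rows in the +28-day column and actual exposure for the rows in that column. Naming both matters, because no single meaning of *received* suits both columns. The causality rule stays as it is. In both partial-date rules, replace the month or year of declaration with the month or year of onset, and otherwise leave the year-only rule unchanged.

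The cost is one sentence and a small programming change, with no new data and no change to the 28 days. State the downside in the SAP: some AEs with a missing day and true onset more than 28 days after stop will also be counted on the stopped drug (46% of those at 29–60 days, under the assumptions above). That is the conservative direction the SAP already takes for other missing AE fields. Using day 15 would be simpler but would still lose 26% of the affected AEs.

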For each patient, the period for notification of adverse events begins from the time when the patient receives the first dose of the study medication or from the date when the patient gives his/her informed consent if he/she has already been exposed to the study medication, and it ends at the end of the observation phase of the study, which is a minimum of 28 calendar days after the last administration of the study medication; the process for declaring the different types of adverse events to the Pfizer/Novartis Pharmacovigilance departments or approved representative during this period are listed in table 4 above. If the patient receives the study medication on the last day of the observation phase, the notification period will be extended by 28 calendar days after the end of the observation phase. Usually, the date when the consent form is signed will correspond to the date that the patient is enrolled in the study.

In some cases, they may be a delay between the date that the consent form is signed and the date of enrolment in the study.

In cases in which the patient gives his/her consent but is never enrolled in the study (for example: the patient changes his/her mind about participating; does not meet the screening criteria), the notification period ends on the date when the decision is made not to include the patient.

If the investigator becomes aware of a serious adverse event occurring at any time after the end of the observation phase that he/she considers to be related to a study medication, this serious adverse event must also be declared to the Pharmacovigilance department at Pfizer.

If an SAE, non-serious AE or specific scenario occurs after the end of the observation phase, it only needs to be declared to the pharmacovigilance department at Novartis, by fax or by e-mail, if the investigator suspects a causal link with the study medication(s).

Assessing causality

The investigator must assess causality and report on it. The investigator must obtain sufficient information to determine the causality of every adverse event. For AE considered to be related to a study medication, the investigator must monitor these events until resolution or stabilisation of the event and/or of any sequelae to the extent deemed to be acceptable by the investigator, and with the approval of Pfizer/Novartis of this assessment.

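### SAP 5.7.2 counts a drug-linked adverse event whatever its date, but its table limits the any, serious and fatal rows to exposure plus 28 days, so related events need not be a subset of any events

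*SAP*

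**What the plan says.** SAP 5.7 plans two presentations of AEs in the safety analysis set: by treatment group at inclusion, and by each treatment received at some point in the study. In the second, an AE belongs to the treatment ongoing when it starts. For an AE that starts after a treatment has stopped, SAP 5.7 defers to a table, which is in 5.7.2.

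The text of 5.7.2 sets rules for the second presentation. The denominator for a drug is the patients exposed to it in the prospective period. There are two routes by which an AE counts. The first is a window: "The AE will be deemed to be on treatment until 28 days after the treatment is stopped". The second is the investigator's judgement: "if the investigator links an AE to a treatment, this will also be counted on this related treatment (regardless of the dates" of intake.

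The table then marks each summary row under one or more of three columns: actual exposure, actual exposure plus 28 days, and the treatment named in the causality field. The rows that matter here are:

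| Row | Exposure +28 days | Causality field |
|---|---|---|
| "At least one adverse event" | marked | blank |
| "At least one serious adverse event" | marked | blank |
| "At least one adverse event resulting in death" | marked | blank |
| "At least one adverse event with a suspected relationship with the study treatment" | blank | marked |

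The related rows that concern discontinuation or dose change carry two marks, actual exposure and causality. The SAP does not say whether two marks mean that both conditions or either condition must be met. A footnote mentions both sources for on-treatment AEs, but in the available text its asterisk is attached to no row.

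**The concern.** The text makes the causality route additional to the 28-day window and does not confine it to the related rows. The table confines it to exactly those rows. Because SAP 5.7 sends events that start after discontinuation to the table, a programmer following the table will depart from the text.

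Safety is one of the three parameters of the primary objective (Protocol 3.1, SAP 5.5), and the tables are meant to describe each drug. Under the table, a drug's serious and fatal rows omit late events that the investigator attributed to that drug. If the patient has moved to another drug, the event appears as serious or fatal under the later drug and not under the one blamed. The related row can also include patients whom the any-AE row leaves out, which makes the summary internally inconsistent.

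**Working it through.** No sample size or power figure is involved, so there is no plan figure to reproduce. The check applies the two rules to the same records.

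**1. One event.** Take an AE linked to drug X that starts more than 28 days after X was stopped.
- Text rule: counted on X in every row it qualifies for.
- Table rule: counted on X in the related row; not counted in the any, serious or fatal rows.

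**2. Set logic for one drug.** Let
- A = patients with at least one AE starting within exposure +28 days;
- B = those of A with at least one AE linked to the drug, at any date;
- C = patients whose only AEs for the drug are linked and start after the window.

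Table rule: any = A, related = B + C. Text rule: any = A + C, related = B + C.

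Under the table, the related patients fail to be a subset of the any-AE patients as soon as C ≥ 1. The related count exceeds the any count only if C > A − B. Under the text, B ≤ A, so B + C ≤ A + C always.

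**3. Assumed records, five patients on one drug.**

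| Patient | Onset relative to last dose | Linked | Serious | Fatal |
|---|---|---|---|---|
| 1 | 30 days before | yes | no | no |
| 2 | 10 days after | yes | yes | no |
| 3 | 40 days after | yes | yes | no |
| 4 | 60 days after | yes | yes | yes |
| 5 | 90 days after | no | yes | yes |

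Table rule: any 2, serious 1, fatal 0, related 4. Text rule: any 4, serious 3, fatal 1, related 4.

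**4. When the related count overtakes the any count.** Assume 35 patients and A = 32, so C is at most 35 − 32 = 3.
- B = 32: C = 1 gives related 33 against any 32.
- B = 30: C = 2 gives 32 against 32; C = 3 gives 33 against 32.
- B = 28: even C = 3 gives only 31 against 32, so it cannot happen.

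**5. Size per row.** Protocol 5.1 plans at least 35 patients each on sunitinib and everolimus and at least 75 on targeted therapies. One patient is 1/35 = 2.9 points, or 1/75 = 1.3 points. A patient adds to the serious row only if no SAE on that drug falls within the window; several late events in one patient still count once.

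**6. Can late events reach the database?** The protocol points both ways.
- Yes: the notification period in Protocol 7 runs to the end of the observation phase, with 28 days after the last dose as a minimum. The data-collection table of the CRF covers every AE observed in the study. CRF 3.4 asks at each visit for all AEs since the previous one.
- No: Protocol 5.2.2 describes safety collection as ending 28 days after treatment stops.

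Neither document gives a count of late related events.

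**The case against.** The fair case on the other side is that the effect is narrow, and much of it stands.

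- **Other related rows.** SAP 5.7.2 and Tables 14.3.2.2, 14.3.2.4 and 14.3.2.8 to 14.3.2.10 also show related AEs by grade and by System Organ Class and Preferred Term (SOC/PT). The attribution table has no lines for these. If they follow the logic of its related row, a late serious grade 3 related event has its own row, and a late related death (grade 5) appears under grade 4 or higher related. The plain serious and fatal rows still omit both.
- **Events do not vanish.** A reader might infer that late related serious and fatal events leave the safety analysis altogether. The documents do not support that. The presentation by treatment at inclusion has no stated 28-day limit, Listings 16.2.6 and 16.2.9 show the events with their causality, and Listing 16.2.12 shows every death.
- **Post-observation reports.** Protocol 7 has a sentence beginning "If the investigator becomes aware of a serious adverse event occurring at any time after the end of the observation phase". A reader might take it as proof that such events are expected in the analysed data. It concerns declaration to a sponsor's pharmacovigilance department and does not say that they enter the eCRF.
- **Alternative reading.** The related row could be how the SAP meant to implement the causality route. The text does not say so, and its wording is additive.
- **The footnote.** It may only explain the rows with two marks. With no visible anchor, it cannot settle the conflict.

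**Conclusion.** The text and the table in SAP 5.7.2 contradict each other for the any, serious and fatal rows of the analysis by treatment received. Under the table, a related AE starting more than 28 days after stopping is absent from the causal drug's three rows while counted in its related row, so the subset relation is not guaranteed. This follows from the two rules alone.

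The size is not known. Each patient whose only serious or fatal event for the drug is late and related shifts that row by one patient, about 2.9 points at n = 35; all other patients shift it by nothing. The 35 is a planned inclusion minimum, and the real denominator may differ because it includes later-line use and recruitment could end short of target. A reader might infer that the related count will exceed the any count. That is only possible, and requires late-only related patients to outnumber in-window patients with no linked AE. The values of A, B and C and the five-patient example are assumptions chosen to show the mechanism.

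The point should be corrected because the rules conflict within a primary-objective analysis and the repair is cheap, not because a large bias has been shown.

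**What to change.** In the SAP 5.7.2 table, mark the causality column for the any-AE, serious-AE and fatal-AE rows as an alternative: an event counts on a drug if it starts within exposure +28 days OR the investigator links it to that drug. Apply the same rule to the matching grade-specific and SOC/PT tables, which the attribution table does not now cover. State for every row with two marks whether they mean AND or OR; otherwise the new marks would be as ambiguous as the existing ones. Attach the footnote to the rows it concerns.

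The opposite repair would also remove the contradiction: restrict the text rule to related rows and add plain serious-related and fatal-related rows. The OR rule is closer to the SAP's present text and guarantees that related AEs are a subset of any AEs.

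The cost is one table edit and one programming condition. The downside is that some rates will read slightly higher, because a few late events are added.
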